## 11.0 Toxicities/Side Effects

11.1 Toxicities will be assessed via the NCI toxicity criteria (CTC 3.0). All toxicities will be recorded in CRDB until 30 days after the last dose of  $^{131}\text{I}$ -3F8.

11.2 Toxicities associated with  $^{131}\text{I}$ -3F8 include fever, headache, nausea and vomiting, pain, allergic reaction, and/or drug extravasation. Hospitalizations for therapy administration, hyperglycemia or lymphopenia related to dexamethasone and self-limited fever, vomiting, or headache will not be considered serious adverse events (SAE) and will not be reported to the IRB or FDA though they will be captured in the institutional database. However, life-threatening infections or other life-threatening side effects will be considered SAE's and will be promptly reported to the Institutional Review Board of MSKCC and to the FDA.

11.3 Neurologic changes during the study period which meet the criteria for grade 4 neurotoxicity will be assessed by study physicians as being unrelated, possibly or probably caused by the injection. In the absence of clear evidence of tumor progression, it may be assumed that new signs and symptoms are treatment related.

11.4 Any deaths will be reviewed during the study by the Principal Investigators prior to subsequent entry of further patients.

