## 12.0 Criteria for Therapeutic Response/Outcome Assessment

12.1 Adequacy of trial: All patients who fulfill the eligibility requirements, receive two treatment injections of  $^{131}\text{I}$ -3F8 and undergo extent of disease evaluation will have an adequate trial.

12.2 The primary endpoint is overall survival at six months from the date of 1st  $^{131}\text{I}$ -3F8 injection.

12.3 Response duration is calculated from the 1st day of treatment with  $^{131}\text{I}$ -3F8.

12.4 Patients developing progressive disease will be considered a treatment failure under this protocol.

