### **13.0 Criteria For Removal From Study**

13.1 If at any time the patient develops grade 4 toxicity (other than controllable fever, vomiting, headache) attributed to the study drugs, he/she will be removed from study and receive no further injections.

13.2 If at any time the patient is found to be ineligible for the protocol as designated in the section on Criteria for Patient/Subject Eligibility (i.e., a change in diagnosis), the patient will be removed from the study.

13.3 If at time disease progression is observed, the patient will be removed from the study.

13.4 If the patient experiences adverse events, including unacceptable toxicity or exacerbation of underlying disease associated with drug administration and necessitating discontinuation of treatment, he/she will come off the study. Patients who are removed from the study due to adverse events will be treated and followed according to established medical practice. All pertinent information concerning the outcome of such treatment will be entered in the Case Report Form or the Serious Event Report, as applicable.

13.5 Withdrawal of consent: The patient's desire to withdraw from the study may occur at any time.

13.6 Noncompliance: If at any time the patient is non-compliant with therapy, radiation safety guidelines or requests withdrawal from the study, he/she will be removed.

13.7 Pregnancy: The patient will be removed from study if they are found to be pregnant.

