#### **14.0 Biostatistics**

This is a phase II study to assess the clinical efficacy of weekly intrathecal  $^{131}\text{I}$ -3F8 for a new cohort of 17 patients with GD2-expressing central nervous system and leptomeningeal neoplasms. A "response" is defined as a patient being alive six months after their first treatment. We will test hypothesis that the proportion of responses is 25% or more against a null hypothesis that proportion of responses is 5% or less, with a power of 80% and an alpha of 5%. Using a Simon two-stage optimal design, nine patients will initially be accrued. If at least one responds, then a further 8 patients will be entered on study. If the total number of responses is three or more, the agent will be declared active. Under this design, the probability of declaring the agent inactive at the end of the first stage (0 / 9 responses) is 0.63 if the true response rate is 0.05. This probability decreases to 0.08 if the true response rate is 0.25. The probability of declaring the agent active (3 or more responses / 17) is 0.05 and 0.8 if the true response rate is 0.05 or 0.25, respectively. It is expected that 4-6 patients/yr will be enrolled and that this study can be completed within 2-3 years.

	Reject null hypothesis if:	Reject alternative hypothesis if:
First stage	-	0 / 9 responses
Second stage	$\geq 3$ / 17 responses	$\leq 2$ / 17 responses

The number of CRs, PRs, SDs and PDs will be reported. Toxicities will be reported by type and grade.

Three additional subgroups will be added for patients with: Medulloblastoma in CR (36 evaluable patients), Medulloblastoma with stable, but minimal disease (36 evaluable patients), and Retinoblastoma or Melanoma (18 evaluable patients). For patients with neuroblastoma or other cancers in the CNS, 18 additional evaluable patients will be added. We have completed the statistics for this agent overall which have shown efficacy on this phase II study; increasing the number of slots will allow for in depth statistical analyses within these subgroups of patients.

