#### **15.1 Research Participant Registration and Randomization Procedures**

#### **15.2 Research Participant Registration**

Confirm eligibility as defined in the section entitled Inclusion/Exclusion Criteria. Obtain informed consent, by following procedures defined in section entitled Informed Consent Procedures. During the registration process registering individuals will be required to complete a protocol specific Eligibility Checklist. The individual signing the Eligibility Checklist is confirming whether or not the participant is eligible to enroll in the study. Study staff are

responsible for ensuring that all institutional requirements necessary to enroll a participant to the study have been completed. See related Clinical Research Policy and Procedure #401 (Protocol Participant Registration).

15.2 Potential risks are outlined above. Procedures to minimize potential risks include prophylactic treatment with acetaminophen, dexamethasone, SSKI drops, liothyronine.. Procedures to minimize radiation exposure to self and others will be in accordance to Radiation Safety Guidelines.

15.3 Enrollment in this protocol is voluntary. In the event of adverse effects, standard medical intervention will be offered where appropriate.

15.4 All hospital records are confidential. The patient's name or any other personal identification will not be used in reports or publications from this study. Laboratory tests, images and X-rays, if any, may be published. The Food and Drug Administration or other authorized agencies (i.e. the National Cancer Institute) may inspect records. Data will be collected and stored in the patient's hospital chart and research file, and be monitored by the principal investigators to ensure the safety of patients.

15.5 There is no extra cost to the patient for being part of this study. If there is an injury as a result of this research study, emergency care, hospitalization and outpatient care will be made available by Memorial Hospital and billed to the patient as part of medical expenses. No money will be provided by the Hospital as compensation for a research-related injury.

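### Section 11.4 holds further entry for review of deaths only; no cumulative count of attributed non-fatal grade 4 toxicity requires a hold over the 108 added patients

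*Combined protocol and SAP*

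**What the plan says.** Section 11.4 contains the only toxicity-related condition on further entry: "Any deaths will be reviewed during the study by the Principal Investigators prior to subsequent entry of further patients." It applies to deaths, including deaths in the expansion, and sets no number.

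For non-fatal grade 4 toxicity the plan provides the following:

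- **13.1:** a patient with grade 4 toxicity attributed to study drug (controllable fever, vomiting and headache excepted) is taken off: "he/she will be removed from study and receive no further injections." Section 4.2.1 likewise makes further cycles depend on the absence of unexpected grade 4 toxicity.
- **11.3:** study physicians attribute grade 4 neurologic change.
- **17.2 and 17.2.1:** grade 4 and 5 toxicities, with listed exclusions, are SAEs and go to the FDA through the IND office. Each report covers relationship, expectedness, whether the event is an unanticipated problem, and whether an amendment is needed. The Principal Investigator signs and dates it.
- **15.4:** data are to "be monitored by the principal investigators to ensure the safety of patients."
- **11.1:** "All toxicities will be recorded in CRDB until 30 days after the last dose of" 131I-3F8.

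Section 14.0 has one interim rule: stop at 0/9 alive at six months, in the 17-patient cohort. It says that the overall statistics are complete, then adds "Medulloblastoma in CR (36 evaluable patients), Medulloblastoma with stable, but minimal disease (36 evaluable patients), and Retinoblastoma or Melanoma (18 evaluable patients", and, for neuroblastoma or other cancers in the CNS, "18 additional evaluable patients will be added." The analysis stated there is: "The number of CRs, PRs, SDs and PDs will be reported. Toxicities will be reported by type and grade."

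**The concern.** Every provision for non-fatal grade 4 toxicity acts on one patient or one report. None looks at the accumulated count and says that entry must wait. Followed as written, accrual could continue through any number of such events, although cumulative toxicity is a stated objective (2.1).

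The original 17 patients had no such count rule either, so the expansion did not lose a safeguard. The gap weighs more there for three reasons. The expansion is over six times larger. No interim rule of any kind applies to it. And a third of it is patients with medulloblastoma in CR, for whom the argument from rapidly fatal disease in section 4.2 does not carry over automatically. At stake is whether the Principal Investigators' general monitoring duty includes a point, fixed in advance, at which they must stop and decide.

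**Working it through.** **1. The plan's own interim figures.** For the Simon design, P(stop at stage 1) = (1 − p)^9, which is 0.630 at p = 0.05 and 0.075 at p = 0.25. P(active) = Σ over x ≥ 1 of P(X₉ = x) · P(Y₈ ≥ 3 − x), which is 0.0466 and 0.812. These match the stated 0.63, 0.08, 0.05 and 0.8. All four concern survival; section 14.0 states no toxicity figure.

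**2. Size of the expansion (14.0).** 36 + 36 + 18 + 18 = 108 evaluable patients. 108/17 = 6.4. 36/108 is one third. 17 + 108 = 125, consistent with the roughly 130 in section 1.0.

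**3. Assumed rates.** The text reviewed gives no grade 4 rate, and part of the phase I background is missing from it. True rates p of 5% to 30% are therefore assumed. The treated number is set to 108; it will be higher if some treated patients are not evaluable.

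**4. Illustrative pooled boundary, taking 10% as tolerable (an assumption).** Hold as soon as the count of affected patients reaches 6 within the first 18 treated, 8 within 36, 11 within 54, 14 within 72 or 16 within 90. There is no trigger after 90. Over paths not yet held, the exact recursion is P(n, k) = P(n−1, k)(1 − p) + P(n−1, k−1)p; mass that reaches the boundary in force at n moves to P(hold). Counts cannot fall, so checking continuously or only at 18, 36, 54, 72 and 90 gives the same P(hold). Only the mean number enrolled differs (57.2 against 60.7 at 20%). The table acts as soon as the count is reached.

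| True rate p | Affected of 108, no rule (108p) | P(hold) | Mean enrolled at first hold or completion | Mean affected by then (p × mean enrolled) |
|---|---|---|---|---|
| 5% | 5.4 | 0.0005 | 108.0 | 5.4 |
| 10% | 10.8 | 0.043 | 105.2 | 10.5 |
| 15% | 16.2 | 0.351 | 87.3 | 13.1 |
| 20% | 21.6 | 0.788 | 57.2 | 11.4 |
| 30% | 32.4 | 0.998 | 25.1 | 7.5 |

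These figures ignore patients entered while toxicity data mature.

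**5. Excess confined to one 36-patient cohort (one patient in three).** Pooled P(hold) is 0.185 if that cohort runs at 30% and the others at 5%, and 0.507 if the others run at 10%. At 20% against 5% it is 0.036. Pooling alone is weak here.

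**6. Separate trigger for the CR cohort.** Hold at 4 within the first 9, 6 within 18 or 7 within 27 of the 36. The same recursion gives P(hold) of 0.001, 0.02, 0.31 and 0.76 at 5, 10, 20 and 30%.

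**7. Unneeded holds with both triggers.** If the rate is 10% everywhere, the chance of at least one is no more than the sum of the two: 0.043 + 0.022 = 0.065.

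**The case against.** The strongest reply is that each event already reaches the right people. Every SAE report needs the Principal Investigator's signature and asks whether the protocol must change. Where IRB submission is required, it is due within 5 calendar days. The IRB, the FDA or the investigators can pause the trial at any time. So a reader who infers that grade 4 events go unreviewed, or that the trial lacks safety oversight, goes further than the documents allow. What remains is narrower: those checks are per event, and none turns an accumulated count into a required hold.

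Second, scheduled looks could come late. At the 4–6 patients per year that section 14.0 gives for the 17-patient cohort, 18 patients take 18/6 = 3 to 18/4 = 4.5 years; no rate is stated for the expansion. This stands against looks at fixed sample sizes, and is why the hold should act as soon as the count is reached.

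Third, a pooled count can miss an excess in the CR cohort, and it tolerates 5/18 (28%) early on. That also stands, and supports a separate CR trigger.

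Fourth, the gain appears at rates above what the visible text suggests. Section 3.4 reports self-limited toxicities and no late ones in five patients off therapy for at least a year, and section 4.2 anticipates no myelosuppression. This is fair and limits the point's weight. The experience is small, though, and section 3.4 also looks ahead to shorter intervals and higher specific activity. If the rate is low, the rule rarely fires.

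**Conclusion.** The gap is real but modest: no cumulative count of attributed non-fatal grade 4 toxicity requires a hold while 108 evaluable patients are added. Closing it is a cheap improvement, between optional and recommended.

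The size depends entirely on assumed rates. At 5% the illustrative pooled rule changes nothing, and at 10% almost nothing. At 20% it forces a review with probability 0.79, after 57 patients on average (those never held counted at 108). At 30% the probability is above 0.99 and the average is 25.

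Two stronger readings are tempting and unsupported. One is that grade 4 toxicity is likely to be frequent; nothing in the visible text says so. The other is that the difference between 32.4 and 7.5 affected patients at 30% is harm avoided. It is not, because accrual may resume after the review. The figures show only when a review becomes compulsory.

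**What to change.** Keep 11.4 as it stands for all deaths. Add to 11.4, with a matching sentence in 14.0:

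*Expansion accrual is held as soon as the number of treated expansion patients with attributed grade 4 toxicity (13.1 exemptions; any onset from the first injection, dosimetry dose included, to 30 days after the last dose) or treatment-related death reaches the boundary, until the Principal Investigators document a decision to resume, modify or stop. The denominator is all patients given at least one injection.*

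- **Pooled boundary (illustration):** 6 within the first 18 treated, 8 within 36, 11 within 54, 14 within 72, 16 within 90. After a decision to resume, the next listed boundary applies.
- **Medulloblastoma-in-CR trigger (illustration):** 4 within 9, 6 within 18, 7 within 27.

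The sponsor should set the tolerable rate and state the operating characteristics in 14.0. The denominator matters because section 12.1 counts as adequate "All patients who fulfill the eligibility requirements, receive two treatment injections of" 131I-3F8 and are then assessed for extent of disease. If evaluability follows that definition, a patient removed for toxicity after one treatment injection would vanish from an evaluable-only count.

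**Cost:** a short amendment that uses the same investigators, the 13.1 event and data already recorded in CRDB. Dosing and individual removal do not change, and no committee is added. The downside is at most about a 6.5% chance of an unneeded review if the true rate is 10% throughout.

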## 12.0 Criteria for Therapeutic Response/Outcome Assessment

12.1 Adequacy of trial: All patients who fulfill the eligibility requirements, receive two treatment injections of  $^{131}\text{I}$ -3F8 and undergo extent of disease evaluation will have an adequate trial.

12.2 The primary endpoint is overall survival at six months from the date of 1st  $^{131}\text{I}$ -3F8 injection.

12.3 Response duration is calculated from the 1st day of treatment with  $^{131}\text{I}$ -3F8.

12.4 Patients developing progressive disease will be considered a treatment failure under this protocol.

12.5 Response Definitions

### 12.5.1 Complete Response (CR)

Cytologic and radiographic CR will be evaluated separately, since patients with cytologic clearing and clinical response may continue to have residual abnormalities on MRI scans. Patients with a CR must also have stable or improved neurologic exam.

- Cytologic CR  
Complete clearing of all malignant cells from lumbar and ventricular CSF based on cytospin preparation in leukemia/lymphoma patients and cytology in solid tumor patients. A cytologic CR must be documented by two negative cytologies on two consecutive occasions at least 4 weeks apart (with no interval positive cytologies).
- Radiographic CR  
In patients with evidence of disease on MRI scan, complete clearing of MRI scan evidence of disease on 2 consecutive scans at least 4 weeks apart will be required.

#### **12.5.2 Stable Disease (SD)**

Exists when a patient fails to fulfill the criteria for either complete or partial response or progressive disease.

#### **12.5.3 Progressive Disease (PD)**

An increase of at least 50% in the absolute number of malignant cells in the CSF OR, in -solid tumor patients, an increase of greater than 25% in the size of measurable lesions on MR scan OR the recurrence of malignant cells in the CSF or new lesions on MR after a patient has attained a complete remission OR evidence of clinical neurologic progression. New sites of or increasing evidence of leptomeningeal enhancement that is not "measurable" will also be considered evidence of disease progression.

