## **8.0 Pretreatment Evaluation**

8.1 Complete history, physical exam, and detailed neurologic exam.

8.2 CBC with differential and platelet count.

8.3 Serum electrolytes, creatinine, AST, total bilirubin, TSH, HAMA, and in child-bearing females, beta-HCG.

8.4 CSF cytology, total protein, glucose and cell count (these are baseline routine, not for research purposes), HAMA.

8.5 Baseline MRI of the brain and spine (with and without gadolinium) within 3 weeks of the first injection.

8.6  $^{111}\text{Indium Ommaya}$  patency/CSF flow study prior to the first injection.

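### Section 12.5.3 does not list a new measurable MR lesion as progression without a prior complete remission, so such a patient defaults to stable disease; CSF conversion from a negative baseline is left ambiguous

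*Combined protocol and SAP*

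**What the plan says.** Section 12.5.3 gives five ways to reach progressive disease (PD):

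1. "An increase of at least 50% in the absolute number of malignant cells in the CSF"
2. In solid tumor patients, "an increase of greater than 25% in the size of measurable lesions on MR scan"
3. "the recurrence of malignant cells in the CSF or new lesions on MR after a patient has attained a complete remission"
4. "OR evidence of clinical neurologic progression"
5. "New sites of or increasing evidence of leptomeningeal enhancement that is not 'measurable' will also be considered evidence of disease progression"

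Only the third carries a condition of prior complete remission. Stable disease (SD) in 12.5.2 is what remains: "Exists when a patient fails to fulfill the criteria for either complete or partial response or progressive disease".

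Section 14.0 reports counts in each response category, section 12.4 labels patients with PD as treatment failures, and section 4.2.2 says that SD may be a sign of response. Sections 4.2.1 and 13.3 act on disease progression. The primary endpoint, in 12.2 and 14.0, is survival at six months.

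**The concern.** A new lesion is ordinarily progression whatever the patient's earlier best response. Here the criterion that names new lesions is tied to an earlier complete remission, and the unconditional last sentence covers only enhancement that cannot be measured. The result is inconsistent: in a patient never in complete response (CR), a new leptomeningeal site too indistinct to measure is PD, while a new nodule clear enough to measure is not listed.

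Because SD is residual, an unlisted event becomes SD by default. Since 4.2.2 treats SD as possible evidence of benefit, the error runs one way, towards apparent activity. The CSF criterion raises a related problem, because it is a percentage change with no rule for a patient whose baseline CSF is negative.

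**Working it through.** **The plan's own design figures.** Section 14.0 states a two-stage rule: stop at 0 of 9; declare the agent active at 3 or more of 17. The chance of stopping early is 0.95^9 = 0.630 at a true rate of 5% and 0.75^9 = 0.075 at 25%. The exact chance of declaring activity is 0.0466 and 0.8122. These match the stated 0.63, 0.08, 0.05 and 0.8. A response in that rule means being alive at six months, so PD does not enter it.

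**The five criteria applied to a patient never in CR.** Case A: a new measurable MR lesion, with known lesions, CSF and neurology unchanged. Case B: CSF cytology turns from negative to positive, with MRI and neurology unchanged.

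| Criterion in 12.5.3 | Prior remission needed? | Case A | Case B |
|---|---|---|---|
| 1. CSF malignant cells up by at least 50% | No | Not met | Undefined at a zero baseline |
| 2. Measurable lesions up by more than 25% | No | Not met lesion by lesion; depends on size if summed | Not met |
| 3. CSF recurrence or new MR lesion | Yes | Not met | Not clearly met |
| 4. Neurologic progression | No | Not met | Not met |
| 5. Non-measurable leptomeningeal enhancement | No | Not met | Not met |

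**Case A, criterion 2.** The text does not say whether size is taken per lesion or as a total, or whether a new lesion enters the total. Let S be the baseline total and m the size of the new lesion, with known lesions unchanged. If new lesions are included, the change is m/S, and PD requires m > 0.25 × S. A smaller new lesion would still be missed, and the ratio is undefined if S = 0. On the lesion-by-lesion reading no new lesion is caught. Case A then falls to SD.

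**Case B, criterion 1.** With baseline count 0 and later count c, the percentage change is (c − 0)/0, which has no value. Rewritten as c ≥ 1.5 × 0 = 0, any positive count qualifies, but so does a count that stays at zero. The clause needs an explicit zero-baseline rule. Criterion 3 does not settle the matter: it speaks of recurrence, and it does not say whether cytologic remission, radiographic remission or both are meant, although 12.5.1 evaluates the two separately. Case B is therefore undefined or PD, depending on the assessor.

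**Is the required count collected?** Section 8.4 lists "CSF cytology, total protein, glucose and cell count" at baseline, without saying that the cell count is of malignant cells. The schedule in section 10 lists CSF cytology before the test dose and at follow-up. Neither specifies a malignant-cell count.

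**The case against.** Several points on the other side stand.

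- A reader might infer that new MRI disease never counts outside remission. It does: the last sentence of 12.5.3 makes non-measurable leptomeningeal enhancement PD unconditionally, and that is a central form of new disease in this trial.
- A reader might infer that CSF conversion is scored as SD. The documents do not support that, because criterion 1 has no remission condition and can reasonably be read as met.
- Case A can still be PD if criterion 2 is read as a total that includes new lesions and the new lesion is large enough, or if there is neurologic progression.
- Section 4.2.1 calls for CSF analysis after treatment, so post-treatment CSF work may go beyond cytology. It still does not specify a malignant-cell count.
- Section 13.3 refers to disease progression without citing 12.5.3, so a shared definition is an inference. The scheduled follow-up MRI and cytology come 1-3 months after the fourth injection, so misclassification at that visit cannot change the four planned injections.
- Patients already in remission at entry, such as the medulloblastoma-in-CR subgroup, are arguably covered by criterion 3.

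None of this closes Case A. The only criterion naming new lesions in general requires prior remission, and no reading of the text explains why a measurable new lesion should count for less than a non-measurable one.

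**Conclusion.** The concern holds in this form. Read literally, 12.5.3 leaves a new measurable lesion in a never-CR patient, with nothing else changed, outside PD and so in SD. CSF conversion from a negative baseline is ambiguous. The effect is on the SD and PD counts reported under 14.0 and on the treatment-failure label in 12.4, and for new measurable lesions it leans towards apparent activity. Six-month survival and the 9/17 rule are untouched.

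The number of patients affected cannot be estimated. It is tempting to add the subgroups other than medulloblastoma in CR, 36 + 18 + 18 = 72, and apply a progression rate. But only the 36 with stable, minimal medulloblastoma are stated to have disease at entry. The preliminary phase II results in section 3 describe patients treated as consolidation, most of whom remained in remission. No document gives a rate of progression by new measurable lesion or by CSF conversion.

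The conclusion assumes that assessors apply the wording as written; those who already count any new lesion as PD would be departing from the text. It should be corrected because a stated rule gives the wrong category and the repair is cheap.

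**What to change.** Revise 12.5.3, for outcome classification and reporting only:

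- Count any new MR lesion, measurable or not, as PD whether or not the patient was ever in CR.
- Count conversion from negative to positive cytology as PD.
- Make the CSF criterion scorable from the scheduled cytology: either replace the 50% clause with a criterion that cytology can supply, or have the malignant-cell count reported on the CSF already drawn at baseline and follow-up.

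Sections 4.2.1 and 13.3, which act on disease progression, should then be reconciled with the revised definition. No treatment or removal rule is proposed here.

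The cost is about one paragraph of protocol wording, with no added scans or CSF samples. The second CSF option adds an item to the laboratory report. The downside is that the PD count may rise and the SD count fall.
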